6.13.6.2. Eosinophilia and Eosinophil-Related AE

In addition to the standard laboratory analysis (Section 6.13.3), eosinophilia and eosinophil-related AE will be summarized. Details regarding eosinophil-related PTs are in Compound Level Safety Standard.

Table KGAK.6.12. Summary Tables Related to Eosinophilia and Eosinophil-Related AE

Analysis	Population
Shift table summarizing the number and percentage of participants within each maximum baseline category versus each maximum postbaseline category by treatment	mS
Summary of eosinophil-related TEAE by PT	mS

Abbreviations: AE = adverse event; PT = preferred term; mS = Modified Safety Population; TEAE = treatment-emergent adverse event.

6.13.6.3. Infections, Including Herpes Infections and Relevant Parasitic Infections

Infections will be defined using the PTs from the MedDRA Infections and Infestations SOC. The MedDRA terms used to identify infections considered to be opportunistic infections (OI) in participants with immune mediated inflammatory conditions treated with immunomodulatory drugs are based on Winthrop et al. (2015) and are listed in the compound level safety standards. The list contains narrow (more specific) and broad (less specific) PTs with respect to these prospectively defined OIs. Definitions of herpes infections, parasitic infections, and skin infections are listed in the compound level safety standards.

Table KGAK.6.13. Summary Tables/Listing Related to Infection Related AE

Analysis	Population
Summary of treatment-emergent infections by PT	mS
Summary of serious infections by PT	mS
Summary of infection AEs resulting in permanent study drug discontinuation	mS
Treatment-emergent AEs, herpes and parasitic infections	mS
Treatment-emergent AEs, skin infection	mS
Summary and/or listing of Infection follow-up form	mS (summary only), S (listing only)
Treatment-emergent potential OI by PT nested with categories for narrow terms and broad terms separately	mS
A listing of participants with potential OI, Serious Infection, Herpes, and Parasitic Infections	S

Abbreviations: AE = adverse event; OI = opportunistic infections; mS = Modified Safety Population; S = Safety Population; PT = Preferred Term.

6.13.6.4. Conjunctivitis

Conjunctivitis are events of special interest and will be identified using PTs nested within the categories of conjunctivitis and Keratitis as described in the Compound Level Safety Standards.

Table KGAK.6.14. Summary Tables/Listing Related to Conjunctivitis

Analysis	Population
Summary of TEAE of conjunctivitis within categories	mS
Summary and/or listing of conjunctivitis and eye inflammation follow-up form	mS (summary only), S (listing only)
A listing of participants with conjunctivitis	S

Abbreviations: mS = Modified Safety Population; S = Safety Population; TEAE = treatment-emergent adverse event.

6.13.6.5. Hypersensitivity

Potential hypersensitivity reactions will be determined using the following SMQs: anaphylactic reaction, hypersensitivity, and angioedema. Potential hypersensitivity will be categorized as immediate (i.e., occurring the same day as drug administration) and nonimmediate (that is, occurring after the day of study drug administration but prior to subsequent drug administration). The planned summaries are provided in [Table KGAK.6.15](#).

Table KGAK.6.15. Summary Tables/Listing Related to Hypersensitivity

Analysis	Population
For immediate hypersensitivity: (1) combined narrow/algorithmic search (that is, any narrow term from any one of the SMQs, or anaphylaxis algorithm); (2) narrow search (that is, any narrow term) by SMQ; (3) broad search (that is, any narrow or broad term) by SMQ; and (4) TEAEs (occurring on the day of study drug administration) by PT not in any of the 3 SMQs	mS
For nonimmediate hypersensitivity: (1) combined narrow search (that is, any narrow term from any one of the SMQs); (2) narrow search (that is, any narrow term) by SMQ; and (3) broad search (that is, any narrow or broad term) by SMQ	mS

Abbreviations: MedDRA = Medical Dictionary for Regulatory Activities; PT = Preferred Term; mS = Modified Safety Population; SMQ = Standardized MedDRA Query; TEAE = treatment-emergent adverse event.

6.13.6.6. Injection Site Reactions

Injection site reactions (ISRs) are AEs localized to the immediate site of the administration of a drug. The evaluation of study drug related ISRs will be through the unsolicited reporting of ISR TEAEs. Injection site reactions will be defined using the MedDRA High Level Term (HLT) of Injection Site Reaction, excluding certain PTs related to joints as described in the Compound Level Safety Standards.

Table KGAK.6.16. Summary Tables Related to Injection Site Reactions

Analysis	Population
Summary of TEAE of ISR overall and by PT	mS

Abbreviations: ISR = injection site reaction; mS = Modified Safety Population; PT = preferred term; TEAE = treatment-emergent adverse event.

6.13.6.7. Malignancies

Malignancies will be defined using PTs from the Malignant tumors SMQ and summarized separately for the 2 categories: Nonmelanoma skin cancer (NMSC) and Malignancies excluding NMSC as below.

Table KGAK.6.17. Summary Tables Related to Malignancies

Analysis	Population
Summary of TEAE of malignancies within categories of NMSC and malignancy excluding NMSC	mS

Abbreviations: mS = Modified Safety Population; NMSC = nonmelanoma skin cancer; TEAE = treatment-emergent adverse event

6.13.6.8. Atopic Dermatitis Exacerbation

Atopic dermatitis exacerbation will be defined using PTs specified in the Compound Level Safety Standards and summarized below.

Table KGAK.6.18. Summary Tables Related to Atopic Dermatitis Exacerbation

Analysis	Population
Summary of TEAE of atopic dermatitis exacerbation	mS

Abbreviations: mS = Modified Safety Population; TEAE = treatment-emergent adverse event.

6.13.6.9. Suicide/Self-injury SMQ

Suicide/self-injury will be defined as described in the Compound Level Safety Standards and summarized below.

Table KGAK.6.19. Summary Tables Related to Suicide/Self-injury

Analysis	Population
Summary of TEAE of Suicide/self-injury	mS

Abbreviations: mS = Modified Safety Population; TEAE = treatment-emergent adverse event.

6.14. Subgroup Analyses

6.14.1. Efficacy Subgroup Analyses

Subgroup analyses will be conducted for the secondary endpoints IGA (0,1), EASI 75 at Week 16 in the mITT Population using the MCMC-MI approach (Section 6.4.1). A logistic regression analysis with treatment, subgroup, and treatment-by-subgroup interaction as factors will be used. The treatment-by-subgroup interaction will be tested using the Firth correction (Firth 1993) at the 10% significance level. Treatment group differences will be evaluated within each subgroup using the Chi-Square test, regardless of whether the interaction is statistically significant. If any group within the subgroup (for example, yes, no) is <10% of the total population, only descriptive statistics will be provided for that subgroup (that is, no inferential testing).

Forest plots may be created to illustrate the treatment differences with 95% CIs between each of the lebrikizumab treatment groups and placebo group, by each subgroup category.

The following subgroups will be analyzed:

- Sex (male, female)
- Race (Asian, Black or African American, White, Other)
- Weight category (<60 kg, \geq 60 to <100 kg, \geq 100 kg)
- BMI category (Underweight [$<18.5 \text{ kg/m}^2$], Normal [≥ 18.5 and $<25 \text{ kg/m}^2$], Overweight [≥ 25 and $<30 \text{ kg/m}^2$], Obese [≥ 30 and $<40 \text{ kg/m}^2$], Extreme obese [$\geq 40 \text{ kg/m}^2$])

- Duration since AD onset category (0 to <2 years, 2 to <5 years, 5 to <10 years, 10 to <20 years, ≥ 20 years)
- Baseline IGA 3 versus 4
- Baseline pruritus <4 versus ≥ 4

Some additional subgroup analyses may be added to meet regulatory requirement. The analysis of additional subgroups will not require an amendment to the SAP.

6.14.2. Safety Subgroup Analyses

Subgroup analysis for safety related endpoints will be performed within the context of the integrated safety analysis. No safety subgroup analysis will be performed specifically for this study unless there is a potentially relevant finding during the periodic study safety reviews.

6.15. Protocol Deviations

Protocol deviations will be identified throughout the study. Important protocol deviations (IPDs) are defined as those deviations from the protocol likely to have a significant impact on the completeness, accuracy, and/or reliability of the study data or that may significantly affect a participant's rights, safety, or well-being. Out of all IPDs identified, a subset occurring during the Treatment Period with the potential to affect primary efficacy analysis will result in exclusion from the PP population.

Potential examples of IPDs include participants who violated the inclusion/exclusion criteria, used an interfering concomitant medication, and significant noncompliance with study medication (<80% of expected injections). Refer to a separate document called "KGAK Trial Issues Management Plan" for the IPDs with categorizations and whether or not these deviations will result in the exclusion of participants from PP set.

The number and percentage of participants having IPD(s) will be summarized within category and subcategory of deviation by treatment group for the Treatment Period using the ITT population.

A by-patient listing of IPDs will be provided.

6.15.1. Impact of COVID-19

Impact of pandemic (for example, COVID-19) on analyses will be systematically addressed prior to study unblinding at Week 16 DBL, once the impact on study conducts are fully understood. In general, any missing assessments/visit window will be documented as protocol deviations. There are no skin efficacy assessments that will be processed or collected in remote visits. Detailed demonstration of "Provisions for Changes in Study Conduct During Exceptional" is in the KGAK protocol. A summary or listing may be provided to summarize missing visits due to COVID-19.

6.16. Interim Analyses and Data Monitoring

Data Monitoring Committee/Data Safety Monitoring Board (DMC/DSMB): The lebrikizumab Phase 3 AD programs' DSMB is an independent expert advisory group commissioned and charged with the responsibility of evaluating cumulative safety at regular intervals, as well as on an ad hoc basis, as needed. The DSMB will consist of members external to Lilly and follow the rules defined in the DSMB charter, focusing on potential and identified risks for this molecule. Data Monitoring Committee membership will include, at a minimum, a physician with expertise in dermatology and a statistician. No member of the DSMB may have contact with study sites. This committee will make recommendations as to a) continue the clinical studies without modification; or b) continue the clinical studies with modifications; or c) terminate one or more of the clinical studies. Details outlining the roles and responsibilities of the DMC are documented in the "Dermira DRM06 DSMB Program Charter" and the planned analyses are outlined in the DMC analysis plan prior to the first unblinded assessment.

Access to the unblinded safety data will be limited to the DSMB. The study team will not have access to the unblinded data. Only the DSMB is authorized to evaluate unblinded data. The purpose of the DSMB is to advise Lilly regarding participant safety; however, the DSMB may request key efficacy data to put safety observations into context and to confirm a reasonable benefit/risk profile for ongoing participants in the study. Hence, there will be no alpha adjustment for these interim assessments.

Week 16 DBL: An unblinded interim analysis will be performed at the time (that is, a cut-off date) the last participant completes Week 16 or the ETV from the study. At the time of Week 16 DBL, the primary endpoint analysis related to booster response to tetanus toxoid has been performed. At the time of Week 16 DBL, the MCV hSBA data is considered as invalid because the assay procedure was not successfully validated at Eurofins Scientific®. Only a small group of statisticians working on the data analysis at the time of the Week 16 DBL had access to the patient-level data. A small internal group of Lilly personnel have been unblinded with a high-level summary result including Global Patient Safety and Medical study team representatives. The patient-level data was quarantined once MCV issues were identified. Personnel who have access to the patient-level data have no access to the biospecimen for the MCV hSBA. The primary endpoint analysis related to MCV response will be on hold until final DBL.

The study will not be terminated early on the basis of efficacy following these interim analyses.

Final DBL: A final DBL will occur after all participants have completed the safety follow-up period of the study, discontinued current study, or enrolled into the long-term extension study DRM06-AD07.

Lilly identified Nixelis as an alternate vendor for analyzing the MCV response using a fully validated rabbit complement serum bactericidal assay (rSBA) in order to deliver results for the final DBL and for analysis. The final DBL will include all data collected by the date of final DBL except Eurofins hSBA data. Final DBL will not occur until new fully validated rSBA is completed by Nixelis and all MCV response data is transferred. The primary endpoint analysis related to booster response to tetanus toxoid will be performed with the Eurofins Tdap data that

is a retransfer of the Week 16 DBL Eurofins Tdap data. The primary endpoint analysis related to MCV response will be performed with the Nexelis retested rSBA data based on the biospecimen collected through Week 16 DBL. For other efficacy and safety analysis, all data collected by the date of final DBL will be included.

6.17. Annual Report Analyses

Based on regulatory requirements for the Development Safety Update Report (DSUR), reports will be produced (if not already available from the study CSR) for the reporting period covered by the DSUR.

6.18. Clinical Trial Registry Analyses

Additional analyses will be performed (if not already available from the study CSR) for the purpose of fulfilling the Clinical Trial Registry (CTR) requirements.

Analyses provided for the CTR requirements include the following:

Summary of AEs, provided as a dataset, will be converted to an XML file. Both serious adverse events (SAEs) and ‘Other’ AEs will be summarized by treatment group and by MedDRA PT.

- An AE is considered ‘Serious’ whether or not it is a TEAE.
- An AE is considered in the ‘Other’ category if it is both a TEAE and is not serious. For each SAE and ‘Other’ AE, for each term and treatment group, the following are provided:
 - the number of participants at risk of an event
 - the number of participants who experienced each event term, and
 - the number of events experienced.
- Consistent with www.ClinicalTrials.gov requirements, ‘Other’ AEs that occur in fewer than 5% of patients/subjects in every treatment group may not be included if a 5% threshold is chosen (5% is the minimum threshold).
- AE reporting is consistent with other document disclosures for example, the CSR, manuscripts, and so forth.

7. Unblinding Plan

Unblinding details are specified in a separate unblinding plan.

8. References

Firth D. Bias reduction of maximum likelihood estimates. *Biometrika*. 1993 ;80(1) :27-38. <https://doi.org/10.1093/biomet/80.1.27>

[PhUSE]. Pharmaceutical Users Software Exchange. Analyses and displays associated with measures of central tendency – focus on vital sign, electrocardiogram, and laboratory analyte measurements in Phase 2-4 clinical trials and integrated submission documents. Published 2013. Accessed June 09, 2020. http://www.phusewiki.org/docs/CSS%20White%20Papers%202016/CSS_WhitePaper_CentralTendency_v1.0.pdf

Appendix 1. Study Visit Mapping for Pruritus NRS, Skin Pain NRS, Sleep-loss Diary and POEM

Pruritus NRS, Skin Pain NRS, and Sleep-loss score are collected as a daily diary; entries will be mapped to study week by the following:

Week	Start Day	End Day
Baseline	Date of First Injection ^a – 7	Date of First Injection – 1
Week 1	Max (Date of First Injection, Week 2 Visit Date – 14)	Week 2 Visit Date – 8
Week 2	Week 2 Visit Date – 7	Week 2 Visit Date – 1
Week 4	Week 4 Visit Date – 7	Week 4 Visit Date – 1
Week 6	Week 6 Visit Date – 7	Week 6 Visit Date – 1
Week 8	Week 8 Visit Date – 7	Week 8 Visit Date – 1
Week 10	Week 10 Visit Date – 7	Week 10 Visit Date – 1
Week 12	Week 12 Visit Date – 7	Week 12 Visit Date – 1
Week 14	Week 14 Visit Date – 7	Week 14 Visit Date – 1
Week 16	Week 16 Visit Date – 7	Week 16 Visit Date – 1

^a If date of first injection is missing, the randomization date will be used.

If multiple assessments on a single day are present, use the first assessment. If an assessment could be mapped to different weeks, it will be mapped to the earlier week. Derivation of the weekly mean scores for Pruritis NRS, Skin Pain NRS, Sleep-loss could be found in [Table KGAK.6.6](#). If at least 1 of the 7 days contains nonmissing daily assessments, postbaseline weekly score will be calculated using prorated weekly average. If the range of 7 days are all missing daily assessments, then the weekly score is missing.

Patient-Oriented Eczema Measure is collected every week via eDiary, the visit week mapping will follow the following rule: the last collected POEM data before the visit date would be used, the evaluation window is injection date –7 to injection date –1 for baseline and visit date –7 to visit date –1 for postbaseline. For example, if a participant gets an injection on the 14th, the scale completed in between the 13th and the seventh would be used.

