1.3. Schedule of Activities (SoA)

The SoA described below should be followed for all participants enrolled in Study KGAK. However, for those participants whose participation in this study is affected by exceptional circumstances (such as pandemics or natural disasters), please refer to Appendix 10.9 for additional guidance.

Notes:												

 Visit 1 procedures may be conducted over more than 1 day as long as all activities are completed within the allowable visit tolerance. For early terminations (ETs) that occur before the last visit in treatment period, see the activities listed for ET in this table. Visit 801 is only for study participants who are terminating early or not rolling into the long-term extension study (DRM06-AD07/J2T-DM-KGAA). 												
Visit number	1	2	3*	4	5*	6*	7*	8	9*	10	ET	V801*
Weeks from randomization	Screening (-4)	Baseline /Day 1	2	4	6	8	10	12	14	16	ET	Safety follow-up Week 26 (or approximately 12 weeks after last study drug injection)
Days from randomization	≤30	—	15	29	43	57	71	85	99	113	N/A	* = visit may be conducted remotely or on site, per preference of the study site or participant. See Section 4.1 for details about remote visits.
Visit interval tolerance (days)		—	±3	±3	±3	±3	±3	±3	±3	±3	N/A	±3
Informed consent	X											
Inclusion and exclusion criteria, review and confirm	X	X										
Demographics	X											
Preexisting conditions and medical history	X											
Prespecified medical history (indication and history of interest)	X											
Review of immunization record	X											Applies only to Tdap, MCV, BCG, or any live (attenuated) vaccine.

Notes:
 
 Visit 1 procedures may be conducted over more than 1 day as long as all activities are completed within the allowable visit tolerance. For early terminations (ETs) that occur before the last visit in treatment period, see the activities listed for ET in this table. Visit 801 is only for study participants who are terminating early or not rolling into the long-term extension study (DRM06-AD07/J2T-DM-KGAA). 													
Visit number	1	2	3*	4	5*	6*	7*	8	9*	10	ET	V801*	Comments
Weeks from randomization	Screening (-4)	Baseline /Day 1	2	4	6	8	10	12	14	16	ET	Safety follow-up Week 26 (or approximately 12 weeks after last study drug injection)	* = visit may be conducted remotely or on site, per preference of the study site or participant. See Section 4.1 for details about remote visits.

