Diary return (patient to site)										X	X		This diary compliance check includes checking for study drug compliance. Participant will need to complete this diary any time the study drug is administered at home (regardless of who administered the drug at home—the participant, caregiver, or mobile home health care provider). Participant would need to visit the site to return the electronic diary. Participants need to return the electronic diary device only if they are not rolling into the long-term extension study (DRM06-AD07/J2T-DM-

Notes:
 
 Visit 1 procedures may be conducted over more than 1 day as long as all activities are completed within the allowable visit tolerance. For early terminations (ETs) that occur before the last visit in treatment period, see the activities listed for ET in this table. Visit 801 is only for study participants who are terminating early or not rolling into the long-term extension study (DRM06-AD07/J2T-DM-KGAA). 													
Visit number	1	2	3*	4	5*	6*	7*	8	9*	10	ET	V801*	Comments
Weeks from randomization	Screening (-4)	Baseline /Day 1	2	4	6	8	10	12	14	16	ET	Safety follow-up Week 26 (or approximately 12 weeks after last study drug injection)	* = visit may be conducted remotely or on site, per preference of the study site or participant. See Section 4.1 for details about remote visits.
Days from randomization	≤30	—	15	29	43	57	71	85	99	113	N/A		
Visit interval tolerance (days)		—	±3	±3	±3	±3	±3	±3	±3	±3	N/A	±3	
													KGAA).
Patient-Reported Outcomes (Electronic Diary at Home)													
Pruritus NRS	Daily (should be completed at approximately the same time every day)												Initial electronic diary entries for Pruritus NRS should be completed a minimum of 4 of 7 days before randomization. PROs should be completed prior to any other study assessments.
Sleep-Loss	Daily (should be completed at approximately the same time every day)												Initial electronic diary entries for Sleep-Loss should be completed a minimum of 4 of 7 days before randomization. PROs should be completed prior to any other study assessments.
Skin Pain NRS	Daily (should be completed at approximately the same time every day)												Initial electronic diary entries for Skin Pain NRS should be completed a minimum of 4 of 7 days before randomization.

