8.1.3.1. Pruritus Numeric Rating Scale (NRS)

Participants will assess pruritus using a Pruritus NRS. The Pruritus NRS is an 11-point scale used by patients to rate their worst itch severity over the past 24 hours, with 0 indicating “No itch” and 10 indicating “Worst itch imaginable.”

Participants will record the pruritus assessments daily using an electronic diary at home. As indicated in the SoA (Section 1.3), initial electronic diary entries for Pruritus NRS should be completed a minimum of 4 of 7 days before randomization.

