Section 6.1.1, Table KGAK.6.2	Added mITT and Modified Safety populations.	See footnote of Table KGAK.6.1.
Section 6.1.2	Baseline period of Pruritus NRS, Sleep-Loss, and Skin Pain NRS was changed from “7-day window on or prior to the baseline visit (Day 1)” to “7-day window prior to the baseline visit (Day 1).”	To exclude the observations collected at baseline visit (Day 1) such that all observations used to calculate baseline are collected before first dose.
Section 6.1.2	Added “There will be no adjustment for multiple comparisons.”	Clarification.
Section 6.2	
Amended to implement the definition of primary and supportive estimands following the ICH E9(R1) addendum.
 
Added the missing data imputation methods relative to each estimand.
	Following ICH E9(R1) addendum.
Section 6.3	Clarified no adjustment will be applied on age group because this study is adult only.	Clarification.

Section	Description of Change	Rationale
Section 6.4	
Amended section to align with the definition of estimands.
 
Clarified each missing data method.
 
Clarified the imputation techniques for each endpoint.
 
Specified the random seeds for each endpoint.
	Clarification. Prespecify random seed.
Section 6.6	Changed analysis population for patient disposition summary table to mITT.	See footnote of Table KGAK.6.1.
Section 6.7.1	
Changed analysis population for demographics and baseline characteristics to mITT from ITT.
 
Removed age group.
 
Removed height.
 
Added “Other nonbiologic medication/treatment” under the “Atopic Dermatitis treatment used in the past” part.
 
Added sleep loss category and skin pain NRS category.
	See footnote of Table KGAK.6.1. KGAK is adult study. To be consistent with other lebrikizumab studies.
Section 6.7.2	
Added Adverse Event eCRF as a source of Medical History records if start date is prior to the first study drug injection.
 
Changed analysis population of medical history to mITT.
	To reflect data collection mechanism. See footnote of Table KGAK.6.1.
Section 6.8	
Changed analysis population of treatment compliance to Modified Safety Population.
 
Added dosing diary as a source counting total number of injections administrated.
	See footnote of Table KGAK.6.1. To reflect data collection mechanism.

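### In SAP Appendix 1 the Week 1 diary mean takes in the day of the first injection when the Week 2 visit is on Day 15 or earlier, so a mostly pre-dose entry dilutes that score

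*SAP*

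**What the plan says.** SAP Appendix 1 maps daily Pruritus NRS, Skin Pain NRS and Sleep-loss entries to study weeks. Baseline ends at "Date of First Injection – 1". Week 1 starts at "Max (Date of First Injection, Week 2 Visit Date", with 14 days taken off the second date and the later of the two used, and ends at "Week 2 Visit Date – 8". If a day has several entries, the first is kept. One non-missing day is enough for a post-baseline weekly score, whereas SAP 6.1.2 requires 4 of 7 days for baseline.

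The revision history for SAP Version 2 takes Day 1 out of the diary baseline and gives the reason: "To exclude the observations collected at baseline visit (Day 1) such that all observations used to calculate baseline are collected before first dose". The same version added the Week 1 algorithm.

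Protocol 8.1.3.1 has participants "rate their worst itch severity over the past 24 hours", and 8.1.3.3 uses the same 24-hour recall for skin pain. Protocol 8.1.3.2 gives no recall period for Sleep-loss. The Schedule of Activities says that "PROs should be completed prior to any other study assessments". It places the Week 2 visit on Day 15 with a tolerance of 3 days either side.

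**The concern.** Version 2 protected baseline from a day that straddles the first dose, but the Week 1 row then assigns that same day to the post-baseline side. Because baseline stops the day before the first injection, Day 1 cannot fall in baseline, and the rule that sends an ambiguous entry to the earlier week does not apply. An entry that looks back 24 hours from Day 1 mostly describes an untreated participant. Averaging it with on-treatment days pulls the Week 1 score toward baseline in both arms and so narrows the expected difference between them.

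At stake is the earliest diary score the SAP derives. Anything that uses it, such as a by-week display or an imputation model, would carry a dilution of known direction.

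**Working it through.** The plan states no figure on this point, so there is none to reproduce. The check applies the Appendix 1 rule to each permitted visit day.

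**Inputs.** D = first injection date = Day 1 (Appendix 1). V = Week 2 visit date, Day 12 to Day 18 (Schedule of Activities: Day 15 ± 3).

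**Window.** Start = max(D, V − 14); end = V − 8. For V = Day 15, start = max(Day 1, Day 1) = Day 1 and end = Day 7. This is a 7-day week, as Appendix 1 intends, with Day 1 inside it. For V = Day 16, start = max(Day 1, Day 2) = Day 2, so Day 1 drops out.

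**Weight and dilution.** With k entries in the window, one of them on Day 1, the Day 1 weight is 1/k. Let c be the mean change over the other k − 1 entries, and assume that the Day 1 entry equals baseline in expectation (not in the documents). The expected Week 1 change is then [(k − 1) × c + 0] / k = c × (k − 1)/k. The last two columns use assumed values of c, for illustration only.

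| Week 2 visit | Week 1 window | Days | Day 1 weight, full diary | Factor | c = −1 becomes | c = −2 becomes |
|---|---|---|---|---|---|---|
| Day 12 | Days 1–4 | 4 | 25.0% | 0.750 | −0.75 | −1.50 |
| Day 13 | Days 1–5 | 5 | 20.0% | 0.800 | −0.80 | −1.60 |
| Day 14 | Days 1–6 | 6 | 16.7% | 0.833 | −0.83 | −1.67 |
| Day 15 | Days 1–7 | 7 | 14.3% | 0.857 | −0.86 | −1.71 |
| Day 16 | Days 2–8 | 7 | 0 | 1 | −1.00 | −2.00 |
| Day 17 | Days 3–9 | 7 | 0 | 1 | −1.00 | −2.00 |
| Day 18 | Days 4–10 | 7 | 0 | 1 | −1.00 | −2.00 |

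For a given visit day, the factor multiplies the mean change in each arm and hence the difference between arms. The average over a whole arm depends on the mix of visit days, which the documents do not give. With full diaries and visits within tolerance, the shrinkage lies between 0 and 25%.

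**Sparse diaries.** With two entries, one on Day 1, the factor is 1/2. If Day 1 is the only entry, it is 0, and the score still counts because one entry suffices. How often this happens cannot be judged from the documents.

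**Later weeks.** The Week 2 window is V − 7 to V − 1. Its earliest start within tolerance is Day 12 − 7 = Day 5. No score from Week 2 to Week 16 can contain Day 1.

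**The case against.** The strongest reply is that nothing planned depends on the Week 1 score. The Schedule of Activities has no Week 1 visit, Table KGAK.6.7 analyses the diary scores at Week 16 and scheduled visits, and the exploratory endpoints in Table KGAK.4.1 are by visit. This stands, and it limits the severity. A reader might infer that an onset claim or the Week 16 secondary results are biased. The documents list no Week 1 comparison and plan no onset claim, and the Week 16 scores do not contain Day 1. An indirect route through imputation is possible but not shown: SAP 6.4.1 does not say whether the Week 1 mean enters the model, and imputation runs separately within each arm.

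Second, the order of diary entry and injection is not fixed. These are home diaries, and the instruction to complete them first concerns assessments, not dosing. An entry made late on Day 1 could look back over both pre-dose and post-dose hours. This also stands: it would be wrong to say that every Day 1 entry is wholly pre-dose. The 24-hour recall and the first-entry rule still make mainly pre-dose content the likely case for itch and pain. For Sleep-loss this is inference.

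Third, Day 1 needs some convention. SAP 6.13.2 counts adverse events on the first dosing day as post-treatment. But an adverse event is dated by onset, whereas a diary rating looks backward, so the convention does not carry over. SAP 6.1.2 itself starts the treatment period after the first injection.

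Finally, the dilution applies to both blinded arms and its expected direction is conservative. That is true, but it does not make the Week 1 score a measure of the first treated week.

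**Conclusion.** The point holds for Week 2 visits on Day 15 or earlier. In those cases the Week 1 mean includes a day that, for itch and skin pain, reflects mostly or wholly pre-dose time; for Sleep-loss this is likely but not documented. With a full diary the expected Week 1 change and treatment difference shrink by about 14% (Day 15 visit) to 25% (Day 12 visit). This rests on Day 1 matching baseline in expectation and is not certain for any one participant. The effect on a 4-point response rate cannot be sized from the documents.

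A reader might take the rule to mean that Week 1 always begins on the injection date. It does not: the 14-day term excludes Day 1 for visits on Days 16 to 18. The consequence is confined to the Week 1 score and to any display or imputation model that uses it. The Week 16 secondary endpoints and the co-primary vaccine endpoints do not contain Day 1. Severity is low.

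**What to change.** In Appendix 1, change the Week 1 start to max(D + 1, V − 14), with D the first injection date and V the Week 2 visit date. Day 1 then belongs to neither baseline nor Week 1.

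SAP Version 3 was approved after the Week 16 database lock, so record this as a dated correction of a derivation, with its reason.

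The change is one line of SAP text and one of programming. It costs one diary day when the visit is on Day 15 or earlier: Days 2–7 (six days) remain for a Day 15 visit and only Days 2–4 (three days) for a Day 12 visit. Windows for visits on Days 16 to 18 do not change. It may also depart from the derivation used in other lebrikizumab studies, with which Version 2 sought to align this appendix.
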